In the future trial, we will need large, generalizable samples that would be difficult, if not impossible, to recruit at one site. Therefore two sites, Washington University and University of Pittsburgh, will participate in the feasibility RCT. Drs. [name] and [name] will serve as principal investigators (PI). The Steering Committee will include the PIs and Drs [name] and [name] (See *Project Leadership Plan*).

Washington University, Study Coordinating Center: The Study Coordinating Center ([name], Director) will oversee personnel training, protocol implementation, data collection and follow-up. [name] is an orthopedic physical therapist with a Master's of Science in Clinical Investigation. As part of her training (K23HD067343), she successfully completed an exploratory trial to assess the feasibility of MPT in the treatment of PAHD. Washington University provides substantial infrastructure to support this project (See *Facilities and Other Resources*). Our multidisciplinary hip group (See *letters [name], [name], [name], [name]*) has substantial expertise in PAHD and experience in participant recruitment for clinical research. The Data Coordinating Center ([name], director) will administer the study, perform scientific oversight, ensure quality control and perform data analysis.

University of Pittsburgh: The Physical Therapy – Clinical and Translational Research Center (PT-CTRC) ([name], Director) will oversee study implementation at the University of Pittsburgh site. [name] will also guide [name] in developing and implementing methods to optimize treatment fidelity among treatment providers. Methods he has used successfully in his previous RCTs will be used in the proposed study. [name] is an experienced investigator and recognized expert in OA,¹⁶ who has conducted multiple RCTs examining the effectiveness of rehabilitation related to lower extremity disorders.^{1, 17, 45} The PT-CTRC provides significant infrastructure to perform multicenter clinical trials including access to potential participants, facilities, equipment and support for new investigators (See *Facilities and Other Resources*).

[figure not shown]

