Secondary outcome – Movement pattern: We will use a digital camera to acquire 2D hip motion while participants complete tasks of varying difficulty: step down, single leg squat, drop vertical jump. Markers will be placed on anatomical landmarks of the pelvis and thigh to assist with hip angle measurement. Previously published procedures²⁵ for camera placement and participant positioning will be used to optimize between-site data collection and reduce the effect of projection angles on the 2D measures. Participants will practice each movement prior to testing. We will then collect 3 trials of each movement. Commercially available software will be used to measure peak hip adduction motion. All measurements will be completed by trained personnel at Washington University, who will be blinded to treatment group.

In our **preliminary work**, we used 3D kinematic methods to quantify hip motion during the single leg squat. For the current study, we chose to use a 2D method that can be easily replicated with simple equipment in the clinical setting. To assess our ability to predict 3D peak hip adduction angle using our proposed 2D method, we used digital videos synchronized to the 3D kinematic data collection. Using data from 12 randomly selected participants, we found the correlation between 2D and 3D peak hip adduction to be high ($r = 0.85$, $P < 0.001$). Test-retest reliability of our 2D method is excellent ($ICC_{3,3} = 0.996$); standard error of measurement of 0.47° .

Randomization: Participants will be randomized to 1 of 2 treatment groups in a 1:1 ratio stratified by sex and HOOS Symptoms quartile (as determined from the preliminary data) within each site. Within each stratum, participants will be allocated using a variable block size so that the desired allocation ratio will be maintained at intervals throughout the recruitment process. Randomization sequences will be generated a priori using a formal probability model and will be elicited from the data capture system. Given the nature of the intervention, it is not possible to blind the treatment providers or participants to treatment assignment. Study personnel performing the assessments or the movement pattern measurements will be blinded to group assignment.

Treatment: Treatment for both groups will include 10 supervised sessions over 12 weeks. After randomization,

[figure not shown]

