Post-treatment assessment: Participants will return for questionnaire completion and movement pattern assessment immediately after treatment. We will compare pre-treatment measures to post-treatment measures of both treatment groups to assess change in functional ability (HOOS) and movement patterns. Additionally, participants will complete a questionnaire developed to determine barriers to treatment adherence and to assess 1) treatment receipt, '*did the participant receive the treatment as intended*' and 2) treatment enactment, '*was the participant able to successfully implement their new skills*'.^{7, 8} To assess sustained effects of treatment, participants enrolled at the Washington University site will return for questionnaire completion and laboratory testing 1-2 years after treatment

Additional measures: We will collect additional measures, to assist in the future trial development. To assess the feasibility of using PROMIS, the NIH-funded Patient-Reported Outcomes Measurement Information System for people with PAHD, we will use the computer-adapted version of the physical function and mobility domains. Using previously reported methods,²³ we will assess hip muscle strength pre- and post-treatment. Finally, using additional funding from Washington University (See letter, [name]), participants will complete study questionnaires, electronically administered, 6 and 12 months after treatment to assess durability of post-treatment improvement.

Sample size considerations: With a sample size of 46 (23/group), the 95% confidence bounds (CBs) around our overall rates of adherence and retention will be between 78% and 96%, meaning that estimates will be within 9% of the true rate. The within site and within group estimates of adherence will be within 13% of the true rate. These calculations assume that the observed rates will be at least 90%, which is reasonable to expect based on our preliminary data. Aim 2 will estimate intervention effect sizes and as such, the study is not designed to generate definitive results. However, with at least 20 participants/group completing pre- and post-testing, the study will have 80% power to detect large effect sizes of 0.9 or above, with 95% CBs between 0.27 and 1.53. We note that preliminary data for the primary outcomes indicate that approximately 50% of the variance in change is explained by the pre-treatment value, and thus power and precision will be increased by including this covariate in the analyses.

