We anticipate no problems enrolling sufficient participants for this feasibility study. We were able to enroll 3-5 participants per month during our previous study. To improve our likelihood of meeting recruitment goals, we have added the University of Pittsburgh site and established collaborations with additional healthcare providers in St. Louis. We have also removed the restriction from the previous study for body mass index (previously <30 kg/m² required for kinematic testing). Support from the Data Coordination Center ([name], Director) will assist in optimizing retention rate and patient follow-up. Additionally, we will provide compensation of \$25/hour to offset travel effort and costs related to the testing sessions and treatment will be provided at no charge.

Statistical Analysis: The primary data analyses for Aim 1 will be descriptive, and include reporting the rate of recruitment, screening, and enrollment for all potential participants considered for the study; and reasons for non-enrollment. Adherence, retention, and fidelity rates will be categorized using the specified thresholds and reported with 95% CBs. Uncategorized rates will be compared between sites and groups by Wilcoxon's test. Aim 2 will generate estimates of effect sizes. We will report change between pre-and post-treatment with 95% CBs. Inferential analyses will compare the change in response to treatment using analysis of covariance (ANCOVA) where change is the dependent variable and the pre-treatment value is the covariate. Accounting for variation in pre-treatment function will increase the precision of the between-group comparisons and also adjust the treatment effect estimates for possible imbalances between groups. If statistical assumptions are not satisfied, transformations will be explored or nonparametric covariance analyses³⁵ will be used.

Data Management and Quality Control: Study data will be electronically captured using the REDCap system hosted in a limited access data center managed by the Data Coordinating Center. Additional quality control programs will verify that study identification numbers are accurately labeled, evaluate consistency over time, and check for incomplete or overdue data. Routine reporting will monitor recruitment and retention, overall quality, and protocol deviations. Throughout the study, standardization of procedures across sites will be ensured by dynamic training and monitoring that includes site visits and remote auditing.

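### Site and sex stratify the randomisation but are left out of the Aim 2 ANCOVA; if either predicts change, the 95% bounds are wider than needed and the test is conservative

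*Combined protocol and SAP*

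**What the plan says.** The Randomization paragraph sets equal allocation to the two arms, "stratified by sex and HOOS Symptoms quartile (as determined from the preliminary data) within each site". Within strata, "participants will be allocated using a variable block size"; the block sizes are not given. The overview of the approach names two sites ("Therefore two sites, Washington University and University of Pittsburgh, will participate in the feasibility RCT"), so there are 2 × 2 × 4 = 16 strata for 46 participants.

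The Statistical Analysis paragraph gives one inferential model for Aim 2: "analysis of covariance (ANCOVA) where change is the dependent variable and the pre-treatment value is the covariate". Nowhere else do the documents add site, sex or stratum to that model. Site enters the analysis only for Aim 1: "Uncategorized rates will be compared between sites and groups".

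Under Sample size considerations, the covariate is justified because "approximately 50% of the variance in change is explained by the pre-treatment value". The same paragraph says of Aim 2 that "the study is not designed to generate definitive results". The closing section on future directions says the effect-size estimates will inform the later large trial.

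**The concern.** Stratified blocking makes the arms more alike on the stratifying factors than chance would, so the treatment estimate varies less from trial to trial than under simple randomisation. An analysis that ignores those factors does not credit this. Whatever site and sex explain is left in the error term, and the model's standard error exceeds the true sampling SD. The bounds come out too wide and the test rejects less often than its nominal 5%.

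The pre-treatment covariate covers the third factor, HOOS Symptoms quartile, only when HOOS Symptoms is the outcome. It does not cover site or sex except through any association with baseline.

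Aim 2's product is an effect size with its 95% bounds, and 20 completers per group leave little precision to spare. The plan already adjusts for baseline to gain precision and to correct chance imbalance. The same reasons apply to factors judged important enough to stratify on.

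**Working it through.** **The plan's own figures.** With 20 per group, SD 1 and a two-sided 5% test (alpha is not stated; 5% matches the 95% bounds), SE = √(2/20) = 0.316. Power at 0.9 is 79.2% (noncentral t, 38 df) or 81.2% (normal), against the stated 80%. The half-width is 0.62 (z) or 0.64 (t), against 0.63 implied by bounds of 0.27 to 1.53. The figures reproduce.

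**The planned ANCOVA.** With baseline explaining 50% of the variance in change, SE = √(0.5 × 2/20) = 0.224 SD. The half-width is 2.026 × 0.224 = 0.453 SD (37 df), and 80% power falls at 0.643 SD.

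**Adding site and sex.** Let r be the share of the remaining 50% that site and sex explain together. If the two are equally strong and each splits evenly, each contributes variance r × 0.5/2, which is a difference of 2√(r × 0.25) SD between its levels. With perfect balance, the ratio of planned to adjusted half-width is t₃₇/(t₃₅√(1 − r)), where t₃₇ = 2.026 and t₃₅ = 2.030. This gives 1.024, 1.052, 1.116 and 1.193 at r = 5%, 10%, 20% and 30%.

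Balance will not be perfect, because 46/16 is about 3 people per stratum and many blocks stay incomplete. The design was therefore simulated with 20,000 trials per setting: 46 randomised in 16 strata with blocks of 2 and 4 (assumed), reduced at random to 20 per group. Power is at 0.643 SD.

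| r (assumed) | Difference per factor | Half-width, planned vs adjusted | Power, planned vs adjusted | Type I error, planned |
|---|---|---|---|---|
| 0% | 0 | 0.453 vs 0.459 | 79.4% vs 78.5% | 4.8% |
| 5% | 0.22 SD | 0.453 vs 0.447 | 79.6% vs 80.5% | 4.5% |
| 10% | 0.32 SD | 0.453 vs 0.435 | 80.0% vs 82.5% | 4.2% |
| 20% | 0.45 SD | 0.454 vs 0.410 | 80.9% vs 86.8% | 3.6% |
| 30% | 0.55 SD | 0.454 vs 0.384 | 81.8% vs 90.8% | 2.9% |

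The adjusted model's type I error is 4.9% throughout. Planned bounds are wider by 0.453/0.435 = 1.04 at 10%, 0.454/0.410 = 1.11 at 20% and 0.454/0.384 = 1.18 at 30%.

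**Mechanism.** In the planned model the mean SE against the true sampling SD is 0.224 vs 0.217, 0.224 vs 0.210 and 0.224 vs 0.202 at 10%, 20% and 30%. In the adjusted model they agree: 0.214 vs 0.215, 0.202 vs 0.203 and 0.189 vs 0.190. Under the null, both models' mean estimates are within 0.001 of zero. When the simulation uses unstratified randomisation instead, the same planned model keeps about 5% type I error. The conservatism therefore comes from stratifying and then omitting the factors.

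**Sensitivity.** With blocks of 4/6 or 4/6/8 (8,000 trials), planned type I error is about 4.2% at r = 10% and 3.6–3.9% at 20%, and planned bounds are about 4% and 10% wider. With a 70:30 site split and a 65:35 sex split (8,000 trials), power is 80.2% vs 82.8% at 10% and 80.9% vs 87.0% at 20%.

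**The case against.** Four points weigh against giving this much importance.

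- **The plan's effect size is 0.9 SD, not 0.643.** At 0.9 the planned ANCOVA already has 97.5% power (SE 0.224, 37 df). Simulated power at 0.9, planned vs adjusted, is 97.4% vs 97.1% at r = 0%, 97.5% vs 98.1% at 10%, 98.0% vs 99.1% at 20% and 98.3% vs 99.6% at 30%. The gain never exceeds about 1.3 points.
- **The stated precision is already met.** The planned half-width of 0.453 is 28% narrower than the 0.63 in the plan (1 − 0.453/0.63).
- **The benefit is assumed.** The documents give no evidence that site or sex predicts change beyond baseline. Break-even is at a share of about 2–3%. Even at 5%, the adjusted bounds are the wider ones in 46% of individual trials. The 20% and 30% rows need differences of 0.45 to 0.55 SD for each factor, although treatment and training are standardised across sites.
- **Comparing Aim 1 rates between sites is a feasibility question.** It does not show that the plan expects site to affect change in HOOS.

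All four points are correct. They limit the importance of the omission. They do not remove the mismatch between design and analysis, and they do not change the direction of its effect.

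**Conclusion.** The concern holds, as a point to consider. Site and sex restrict the randomisation and are absent from the only Aim 2 model. If they predict change beyond baseline, the planned bounds are too wide: by about 4% at a 10% share of the remaining variance and about 11% at 20%. Type I error falls to about 4.2% and 3.6%. Below a share of about 2–3% nothing is gained.

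These sizes rest on the plan's 50% for baseline and 20 completers per group, on assumed block sizes, and on an assumed prognostic strength for site and sex. The treatment estimate is unbiased, the error is conservative, and no precision or power figure in the plan fails. What is at stake is unused precision in the estimate that the later trial will draw on.

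**What to change.** In Statistical Analysis, specify the Aim 2 model as change = treatment + pre-treatment value + site + sex, fixed before outcome data are seen. Use main effects only; indicators for 16 strata would use too many degrees of freedom with 40 completers.

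The cost is one sentence, no new data (both factors are already recorded for randomisation) and 2 of 37 residual degrees of freedom. If neither factor matters, the bounds are about 1% wider and power at 0.643 SD falls by about 1 point.

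Optionally, when the outcome is not HOOS Symptoms, add the continuous baseline Symptoms score, at the cost of a third degree of freedom. The documents do not show that it helps. In simulation (8,000 trials, site and sex share 10%, assumed correlation of 0.5 with the outcome's own baseline), it costs 0.8 power points if it adds nothing (81.9% to 81.1%). It gains 3.7 points if it explains 10% of the post-baseline variance (82.0% to 85.7%).

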Appendix 3: Movement Pattern Training Protocol

3.1 Task-specific instructions

- Handouts provided to participants to reinforce performance of task-specific modifications during daily activities.

3.2 Progression table for task-specific training

- Provides overview of progression for task-specific training.

Appendix 3.1

Sitting Down From Standing Position

1. Stand with knees touching back of chair, feet hip-width apart.

2. Bend at your hips and knees while simultaneously contracting your thighs to slowly lower yourself onto the chair.

- 3a. Keep your knees aligned with your feet.

- 3b. Don't allow knees to roll in. Squeezing your buttocks will prevent your knees from coming together.

4. Sit down onto the front of the chair and scoot to back of chair

If can't bend hip past 90 degrees, straddle feet so the _____ foot is back and the _____ foot is forward.

Standing Up From Sitting Position

1. Position your feet hip-width apart and far enough under you so there is a good bend at your knees.
2. Scoot to the front of the chair. Position your feet slightly behind your knees.

3. Use your thighs and buttocks to lift your body up off the chair while shifting weight forward. Avoid pulling your knees back to meet your body.

[figure not shown]
[figure not shown]
4. Keep the knees aligned with the toes. Do not allow the knees to roll in.

5. Final position of your knee should be relaxed with a slight bend.

If you can't bend hip past 90 degrees, straddle feet so the _____ foot is back and the _____ foot is forward.

Walking

Focus on moving in a heel to toe fashion, keeping feet hip width apart.
Avoid pivoting on a fixed foot.

[figure not shown]

Try to let your heel land softly on the ground. Contract your seat muscles as the heel hits the ground to align knee over foot.

Avoid completely straightening your leg from the point your heel hits the ground to the point where your toes leave the ground; always have a bend in your knee.

[figure not shown]
- decrease speed
- decrease stride length

Make sure you “lift your heel” to help make pushing off with your toes easier. Taking slightly shorter steps can also help.

Ascending Stairs

Lean forward and use your thigh and buttock to move your body forward onto the next stair. Avoid pulling your knee back to meet the body. Instead propel the body forward on to the next stair.

Squeeze your buttock to prevent your knee from turning inward.

Correct

Don't let your knee roll in or your pelvis tilt.

Incorrect

Note: If ascending stairs is painful, use a handrail or step up each step with your non-painful leg first

Descending Stairs

Lean forward and bend your standing leg to slowly lower yourself onto the next stair.

Squeeze your buttock to prevent your knee from turning inward.

Correct

Don't let your knee roll in or your pelvis tilt.

Incorrect

Note: If descending stairs causes pain, lead each stair's descent with the painful hip.

Weight Shifts

Weight shifting with unilateral gluteal contraction of the stance limb

Purposes:

- To improve the performance of the hip external rotator and abductor muscles.
- To prevent compensatory movements of the hip, pelvis, and spine.
- To prevent the thigh from turning inward.

1. Stand with both feet relatively close together.
2. Shift your weight to one leg.
3. Tighten your buttock muscle on the side of your stance leg.
4. Repeat to the opposite leg.
5. Alternate the weight shift from one leg to the other.
6. Keep your pelvis level and trunk upright.
7. Do not let your opposite hip drop.
8. Do not let your knee turn inward.
9. You may place your hands on your pelvis to monitor your motion.

Repeat 10-20 times on each leg. Perform 2 sets.

*this exercise may be used frequently throughout the day to improve contraction and reduce pain.

Single leg stance

Single leg stance

Purposes:

- To improve the performance of the hip external rotator and abductor muscles.
- To prevent compensatory movements of the hip, pelvis, and spine.

1. Stand with both feet relatively close together and knees “unlocked”
2. Shift your weight to one leg and tighten your buttock muscle on the side of your stance leg.
3. Lift your opposite leg in front of you as if marching in place.
4. Repeat to the opposite leg.
5. Keep your pelvis level and trunk upright.
6. Do not let your opposite hip drop or knee turn inward.
7. You may place your hands on your pelvis to monitor your motion.

*Optional: Hold onto countertop for balance

Repeat 10-20 times. Perform 2 sets.

Single Leg Squat

Lean forward and bend your standing leg to slowly lower yourself and return to the starting position.

Squeeze your buttock to prevent your knee from turning inward. Keep your trunk in the upright position.

Correct

Don't let your knee roll in or your trunk bend to the side.

Incorrect

Standing

Don't stand with your knees locked. Allow there to be a slight bend in your knees.

[figure not shown]

Correct

[figure not shown]

Incorrect

Don't stand with your hips swayed forward or your shoulders swayed back behind your hips.

Correct

[figure not shown]
Incorrect

Don't stand with weight on one leg:

Incorrect

Instead, stand with equal weight on both legs with your feet hip width apart:

Correct

Avoid standing for prolonged periods.

Allow feet to point out if femoral retroversion

Allow feet to point in if excessive femoral anteversion

Sitting

Position yourself so that your knees are aligned with your feet. While sitting, your feet should be supported (flat on the floor). Back rest should be supportive.

Your therapist may instruct you to sit with your hips higher than your knees. You may need to raise your chair or use a pillow or wedge in your chair.

Don't sit with your knees higher than hips.

Don't rest feet on toes pulled underneath chair.

Don't sit in a "W" position

Don't cross your legs in any of the following positions:

(a) Leg around thigh.

(b) Thigh over thigh.

(c) Ankle over knee

(d) Sitting on one leg

Sleeping

When sleeping on your side, use pillows between your knees
to keep your legs parallel to the floor:

Incorrect

Correct

Avoid extreme hip flexion or rotation:

Incorrect

Incorrect

Additional instructions:

- _____ When sleeping on your stomach, place a pillow under your hips.
- _____ When sleeping on your back, place a pillow under your knees.
- _____ When sleeping on your side, you may reduce pressure on your hip by
 - _____ placing towel rolls above and below the hip bone.
 - _____ a towel roll under the waist.

